MATEC affiliated clinics in the Midwest region are eligible to participate in Aim 1 if meeting these criteria: (1) Clinic must have at minimum 40 current patients who are: racial/ethnic minority AND have a 'detectable' viral load AND are aged 16-35 years; (2) clinic must be willing to commit at least one staff person as lead for registering clients to receive the intervention, completing consent, and administering research surveys; (3) clinic must be willing to provide deidentified individual-level data for registered TXTXT participants, including viral load, retention in care (dates of clinic visits) at least twice per year; (4) clinic must not be using a competing medication reminder text messaging system; (5) clinic must be willing and able to rely on Lurie IRB. Once sites sign a memorandum of commitment, the study coordinator will schedule a conference call to conduct a standard of care questionnaire (Appendix K). The standard of care questionnaire will document existing clinic approaches to support adherence as well as any ancillary services (e.g., transportation assistance). This information will form a descriptive profile for each clinic.

Study Inclusion

For inclusion in the TXTXT intervention individuals must meet the following criteria: 1) diagnosed with HIV-infection and on ART regimen for at least one month (not new to ART); 2) aged 16-35 years; 3) have a viral load ≥ 200 c/mL and/or report poor adherence (<90% of pills taken in the last 30 days); 4) able to receive text messages; 5) provide informed consent for research component; and 6) are a patient of a participating clinic

Study Exclusion

Exclusion criteria includes: 1) those who are unable to give informed consent 2) those who are participating in other studies that impact primary and secondary outcomes.

Procedures for Recruitment and Informed Consent

Aim 1: Youth living with HIV (aged 16-35 years) who meet study inclusion criteria will be recruited by study staff from participating clinics. The EMR will identify potentially eligible patients who will be invited to complete further study screening and enrollment.

We will ask each clinic to construct a list of eligible patients and carefully track outreach, screening, and enrollment on an enrollment log provided. Clinics may enroll up to 50 participants (to account for 20% attrition, final sample of 40 participants per clinic).

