Participants will be contacted either by phone or in-person by staff members at participating clinics using the recruitment script/screener (Appendix C). If potential participants are interested in enrolling in the study (Aim 1), staff members at participating clinics which have received Institutional Review Board (IRB) certification will conduct eligibility assessment and consent conferences with participants. Potentially eligible participants will be contacted by clinic staff who will screen them for eligibility and further consent and enroll them if eligible (Appendix C). Those individuals who are ineligible will be thanked for their time.

Lurie Children's IRB will ensure that the consent forms meet institutional and funding source standards. Lurie Children's requires that research participants review and sign an informed consent form. Participants aged 16-17 years will sign an assent form (a waiver of parental consent will be obtained prior to study start). Participants aged 16-17 years are eligible to provide assent in all participating clinics. The informed consent forms include information about the overall purpose of the study, study procedures, potential risks, potential benefits to participating for individuals and society, alternatives to participating in the study, confidentiality of data, and contact information for the site's Principal Investigator and the IRB (Appendix L). Once informed consent has been obtained, the clinic staff will have the form reviewed by a fellow team member, who will confirm that it is fully completed before it is filed in a secure location under double-lock when not in use and with restricted access during work hours and/or when unattended.

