Project staff will inform participants that they have the right to skip any questions that make them feel uncomfortable. Participants will be informed that participation is completely voluntary and that they are free to stop their involvement in the study at any time without any negative consequences. Participants can stop their text messages by replying "STOP" at any time or by calling the participating clinic to unenroll in the study. Participants will be informed of their rights to privacy and confidentiality and will be told that their answers to the survey (collected via computer-assisted self-interview [CASI]) will be kept confidential and not shared with others outside of the research staff. They will be informed that no information about them or provided by them during the research will be disclosed to others without their written permission, except if necessary to protect their rights or welfare (for example, if they are injured and need emergency care) or if required by law (i.e., child or elder abuse, harm to self or others).

Dependent on site randomization, intervention sites will sign up eligible participants to receive automated SMS messages from the DimagiCommCare platform. Participants will have the option to tailor the message content based on their own preferences and will be able to select to receive messages in English or in Spanish. The time the messages are delivered, and frequency will also be selected. Clinic staff will use the text message tailoring form to record tailored messages (Appendix D). Clinic staff will enter information from this form into the text messaging platform, and then test receipt of text messages by the participant before they complete this first intervention visit. If the participant chooses a text message that discloses their HIV status, clinic staff will guide participants into selecting a discrete message and discuss options for alternate text. Participants at control sites will receive standard of care adherence counseling but will not enroll in text messaging until their site is eligible to receive the intervention. Messages used previously include, "Have you taken your vitamins

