Retention will be facilitated through obtaining contact information for the participant during the initial stages of the enrollment process. To minimize participant and staff burden, the follow-up visits can be conducted virtually. Participants will be sent a personalized link to complete the follow-up survey via REDCap. Of note, there will not be financial reimbursement for participation in the

intervention as the goal of the project is to understand how TXTXT will work in the “real world” and inform wide scale routine implementation. Prior studies by Drs. [name], [name], and [name] with vulnerable adolescent and other marginalized populations have maintained >80% retention. We will employ best practices in participant retention including: 1) collecting extensive locator information (multiple addresses/emails, phone numbers, social media profile names, etc.); 2) identification and discussion of difficult-to-reach participants and potential solutions during weekly team meetings; and 3) maintaining flexibility with mode of follow-up (e.g., in person options as well as internet based). The investigative team and participating clinic staff will review the study team’s retention plans and will be asked for guidance on how to best keep YYALH engaged in the study for at least 6 months. No financial incentives will be provided to youth participating in the TXTXT intervention trial (Aim 1). At 3 months, 6 months, and 12 months post baseline, electronic medical record (EMR) data from participating clinics will be used to determine viral load; retention in care will be assessed for up to 12 months post baseline.

STUDY DESIGN AND DATA ANALYSIS

Study participation summary

1. 12 participating clinics randomized 1:1 into intervention or comparison arm
2. 50 participants at each clinic enrolled and complete baseline survey; baseline EMR data pulled
3. Participants at intervention clinics begin TXTXT after baseline survey and continue for 6 months
4. All participants complete a 3-month survey
5. Participants at comparison clinics begin TXTXT after 3-month survey and continue for 3 months
6. All participants complete a 6-month survey; 6-month EMR data pulled
7. TXTXT intervention stops at 6 months post baseline for all participants
8. 12-month EMR data pulled

Timepoint	Who	What	Data collected
zero	12 participating clinics	Randomized 1:1 intervention: comparison arm	

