baseline	50 participants at each clinic	Participants at intervention clinics receive TXTXT	EMR data Baseline survey
		Participants at comparison clinics do not receive TXTXT (i.e., standard of care)	
3 months	50 participants at each clinic	Participants at intervention clinics continue with TXTXT	3-month survey
6 months	50 participants at each clinic	Participants at comparison clinics begin TXTXT TXTXT stops for all participants	EMR data 6-month survey
12 months	50 participants at each clinic		EMR data

Sampling

We will ask each clinic to construct a list of potentially eligible patients and carefully track outreach, screening, and enrollment on an enrollment log provided. Participants (N=600, n=50 per each clinic site) will be enrolled.

The list of potentially eligible patients will be constructed from available EMR data and will be queried based on: (1) diagnosed with HIV; (2) age range (16-35 years); (3) most recent viral load obtained in past 12 months. If potential participants meet the first two criteria, they will be evaluated based on (#3) viral load data. The following scenarios are possible: 1) potential participant is virally suppressed; 2) potential participant is viremic (>200 copies/mL); 3) potential participant does not have viral load data available. Patients who are viremic and meet criteria 1-3 (HIV status, age) will be considered eligible for study inclusion and will be called by clinic staff to confirm eligibility and assess interest. Patients who meet criteria 1 and 2 and are virally suppressed or missing viral load data will be contacted to assess eligibility - specifically, those who are virally suppressed will be queried about medication adherence (if <90% of pills taken in the past 30 days); for those who are missing viral load data they will be asked if they are willing to re-engage in HIV care and have labs drawn prior to enrollment (if so, they will follow steps outlined above for those with viral load

STUDY DESIGN AND DATA ANALYSIS

(VL) data). The list and eligibility assessment will be documented and reviewed on a weekly basis with individual sites to ensure timely enrollment into the study.

Data Analysis Plan and Variables

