The data manager and study coordinator will review the Dimagi platform data reports, which include logs of all texts sent, received, responded to, as well as a log of “STOP” requests. These reports will be pulled by week and by clinic. The data manager and study coordinator will provide summary data to clinic sites as well as action items (e.g., follow up with “STOP” participants to inquire if they would like to discontinue from the study, or stop their messages for short time period). Summary statistics will be provided monthly as process data for the entire study team to review.

Sites in the control arm will continue the standard of care, which will include traditional adherence counseling. Data from the EMR will be gathered for both the control and intervention site participants to include viral load and visit attendance.

At baseline, univariate analyses will be used to characterize the sample; and bivariate analysis will be employed to explore any differences between groups (e.g., differences between clinics; age categories; sex). Fisher’s Exact Test and χ^2 tests (for categorical variables) and t-tests (for continuous variables) will be used to identify demographic and behavioral factors associated with adherence and retention in care. Generalized linear models (GLMs) will be used to assess the effect of the intervention on the outcomes between the intervention and the control arm at 3 months and pre-post differences in the control arm after received the intervention at 6 months. GLMs can accommodate dependent variables with normal, binary, Poisson, and negative binomial distributions and can be adapted to incorporate random and fixed effects (generalized linear mixed models; GLMMs) to account for within-subject correlation among repeated measures over time.³¹ The generalized estimating equation (GEE) can be used to compare ‘average’ population-level response to the intervention.³² Potential confounding and effect modification by sociodemographic characteristics and location (defined by urban vs. rural residence) will be examined in exploratory analysis and these variables will be selected for inclusion in multivariable models based on statistical significance and conceptual importance. All models will account for correlation among repeated measures on individuals and within sites over time as appropriate. Inclusion of random effects for intercept and trend over time will be explored to assess subject-specific variability.

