7. Aside from eligibility criteria, does the volunteer appear to be a good fit for the project? Yes
 No (*Check ineligible and briefly explain below*) Ineligible

INSTRUCTIONS: If any of the above ineligible boxes are checked, read the INELIGIBLE script. If none of the ineligible boxes are checked, read the ELIGIBLE script below.

SCRIPT FOR INELIGIBLE VOLUNTEERS:

Participants for this project are selected based on the questions you were just asked. Based on your answers, it turns out you're not eligible to participate. Thank you for taking the time to talk with me about our project.

SCRIPT FOR ELIGIBLE VOLUNTEERS:

Thank you very much for the information you provided. Based on your answers to these questions, you are eligible to participate in this project. That means that if you want to participate in the text message project, you may. Do you think you might be interested in taking part in this project?

Response: If "NO", thank them for their time. If "YES":

Before we go any further, I need to get your name and birthdate, then schedule an appointment with you.

Participant Name*: _____ Date of Birth*: _____

Month Day Year

CONFIRM AGE GIVEN WITH DOB

* With the completion of this box, this document now contains confidential identifying information and should be securely filed with other confidential identifying records for this participant (e.g., Contact Information Sheet, Consent/Assent Form).

RECRUITER INITIALS: _____ **SCREENING DATE:** _____
Month Day Year

What's a good time for you to come in? _____ at _____ : _____ AM /PM

And if we miss you at that time, what's a good way to contact you to follow up? Phone:

What's your cell phone provider? _____

Ok to leave a voicemail message?

Just as a reminder, we need you to bring your cell phone with you to the visit because if you are randomly chosen to receive texts, we will test the text message system with your phone.

Email:

Ok to email?

Investigator/Designee

Signature

Print Name

Date

Entered into screening database

Screening ID: _____

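### The Appendix C screener lets clinic staff, after their clinic is randomised, turn away volunteers on an open 'good fit' judgement that is in neither eligibility list (minor)

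*Combined protocol and SAP*

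**What the plan says.** **Order of events.** The Study participation summary lists as step 1 "12 participating clinics randomized 1:1 into intervention or comparison arm" and as step 2 "50 participants at each clinic enrolled and complete baseline survey; baseline EMR data pulled". The timepoint table agrees: randomisation is at 'zero' and participants enter at 'baseline'.

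**Who selects.** Under Procedures for Recruitment and Informed Consent (Aim 1): "Potentially eligible participants will be contacted by clinic staff who will screen them for eligibility and further consent and enroll them if eligible". The same section gives staff work that depends on the arm: "Dependent on site randomization, intervention sites will sign up eligible participants to receive automated SMS messages". Control sites do not register participants for texting until they cross over. The documents describe no concealment of the allocation from recruiters and do not say when a clinic learns its arm.

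**The item.** In Appendix C, the interviewer-only block is headed as questions 14 to 18 but its five items are printed as 3 to 7. The last one (printed 7, hence item 18, and not the cell-phone question that is also numbered 7) reads "Aside from eligibility criteria, does the volunteer appear to be a good fit for the project". A 'no' means marking the volunteer ineligible with a brief explanation, and any single ineligible mark leads to the ineligible script.

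**The protocol lists.** Study Inclusion has six criteria and none concerns fit. Study Exclusion begins "Exclusion criteria includes: 1) those who are unable to give informed consent 2) those who are participating in other studies" and has only those two grounds, the second limited to studies that affect the outcomes.

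**Records and checks.** Clinics keep an enrolment log. Appendix C has all answers recorded even for ineligible volunteers. Under Sampling, the list and eligibility assessments are documented and "reviewed on a weekly basis with individual sites to ensure timely enrollment into the study". In the Aim 1 Data Analysis Plan, "bivariate analysis will be employed to explore any differences between groups" at baseline, and confounding is examined in exploratory models.

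**The concern.** In a cluster trial that recruits individuals after allocation, randomising clinics protects the comparison only if entry to the sample does not depend on the arm. Most screener items have factual content. This one has none: by its own wording it applies outside the criteria, and it is decided by someone who probably knows what the volunteer will receive. If staff in one arm turned away people they expected to do badly more often than staff in the other arm did, the 3-month adherence comparison would carry a difference that TXTXT did not cause.

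The planned safeguards record or may partly reveal such exclusions, but they do not prevent them. None is stated to be done blind to arm. The reach measure compares enrolled with eligible patients but is not described as by arm, and no by-arm report of exclusions is planned. Exploratory covariate adjustment with 12 clinics cannot be relied on to correct selection on unmeasured motivation.

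**Working it through.** **Step 1: the plan's own power figure, to obtain a usable standard error.** Inputs from the sample size section: 6 sites per arm, 40 analysed per site, 2 measures per participant, correlation 0.05 within site and 0.2 within participant, type I error 0.05 (taken as two-sided).

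- Design effect = 1 + 2 × (40 − 1) × 0.05 + (2 − 1) × 0.2 = 5.1.
- Effective number per arm = 6 × 40 × 2 ÷ 5.1 = 480 ÷ 5.1 = 94.1.
- Two-proportion power for a 20-point difference, by control rate: 0.826 at 25%, 0.792 at 35%, 0.792 at 45% and 0.826 at 55%. Table 2 states 0.82 at 25%, 0.80 at 35%, 0.80 at 45% and 0.83 at 55%. It reproduces.
- Standard error implied by the 35% cell: the normal quantiles for a two-sided 5% test and 80% power are 1.960 and 0.842, with sum 2.802, so SE = 20 ÷ 2.802 = 7.14 points. All 12 cells of Table 2 imply 6.7 to 7.3 points.

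**Step 2: false difference from a veto used in one arm only.** Let p be the control adherence rate, s the share of future non-adherers removed and f the share of future adherers removed, with no true effect.

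- Bias = p(1 − f) / [p(1 − f) + (1 − p)(1 − s)] − p.
- Vetoes per 50 enrolled = 50 / [1 − (1 − p)s − pf] − 50; multiply by 6 for one arm.
- False-positive rate: normal approximation, two-sided 5% test, SE 7.14 points.

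Worked case, p = 0.35, s = 0.10, f = 0.05. Adherers kept: 0.35 × 0.95 = 0.3325. Non-adherers kept: 0.65 × 0.90 = 0.585. All kept: 0.9175. The adherence rate among those kept is 36.24%, so the bias is 36.24% less 35%, or 1.24 points. To enrol 50, a clinic must screen 50 ÷ 0.9175 = 54.5 otherwise eligible volunteers, so there are 4.5 vetoes per clinic, or 27 over six clinics.

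| Removed: non-adherers / adherers | Bias (points) | False-positive rate | Vetoes, six clinics |
|---|---|---|---|
| 5% / 2.5% | 0.59 | 5.1% | 13 |
| 10% / 5% | 1.24 | 5.35% | 27 |
| 20% / 10% | 2.72 | 6.7% | 59 |
| 5% / none | 1.18 | 5.3% | 10 |
| 10% / none | 2.43 | 6.3% | 21 |
| 20% / none | 5.23 | 11.3% | 45 |
| none / 10% | −2.36 | 6.3% | 11 |

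The first three rows let staff predict imperfectly, with non-adherers removed at twice the rate of adherers. The next three assume perfect prediction, because no future adherer is ever removed. The last row shows the sign reversing when the people removed are future adherers.

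Across control rates of 25% to 55%, the first three rows give 0.5 to 0.6 points, 1.0 to 1.3 points and 2.3 to 2.9 points. If both arms apply the same s and f, the bias is zero.

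**What is assumed.** The documents give no veto rate, so every s and f is my assumption. They also give no control rate for viral suppression, so the illustration covers adherence only.

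**The case against.** The strongest reply is that this is a small matter in an openly allocated cluster trial.

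- **The documents push against vetoing.** The protocol hypothesises a reach of at least 80%. Clinics can qualify with as few as 40 suitable patients yet may enrol 50. Each veto needs a written reason, and eligibility assessments are reviewed weekly. The 20%/10% case needs about 59 vetoes in one arm and none in the other. This stands.
- **Under imperfect prediction the effect is small.** At modest veto rates, the false-positive rate moves from 5% to between 5.1% and 5.35%. This stands.
- **Two premises are inferred.** Staff knowledge of the arm follows from clinic-level allocation and arm-specific tasks and is stated nowhere. Nothing in the documents suggests that the arms would use the item differently. This stands too. The closing script tells volunteers they may be randomly chosen to receive texts, but that does not show that staff are unaware of the arm; it only misdescribes allocation by clinic.
- **Deleting the item leaves other discretion.** The same staff still carry out outreach and consent, and still judge cognition, distress and intoxication. This stands against any claim that the route would be closed. It is no reason to keep the one item that has no defined content.

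A reader might infer that removing the item would bring Appendix C into line with the protocol criteria. It would not. Item 13 rules out volunteers with few missed doses without regard to viral load, whereas the third inclusion criterion admits people on viral load, reported poor adherence, or both. The items on language, never texting, distress and intoxication also go beyond the protocol lists.

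**Conclusion.** The point holds as a minor one. The form contains an open-ended exclusion that the protocol criteria do not, and it is applied after randomisation by staff who probably know their arm. That mismatch is in the text and does not depend on any argument about bias.

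A reader might go further and infer that the trial's comparison is biased, or take 5.2 points as the worst case. The documents support neither reading. They do not show that the item will be used, that its use would differ by arm, or in which direction. The 5.2-point figure assumes perfect prediction and a chosen 20% veto share, so it is not a bound. With imperfect prediction and modest one-arm vetoing, the illustration gives about 0.6 to 1.2 points, against a standard error of about 7 points and a design difference of 20 points. The case for change is that the route is avoidable and cheap to narrow.

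**What to change.** 1. Delete the last interviewer-only item of Appendix C as an eligibility gate. Leave the cell-phone question, also numbered 7, in place.
2. From the existing enrolment log and screening forms, tabulate by arm the numbers screened, excluded (with reasons) and enrolled.
3. As a minor wording correction, change the closing script line on being randomly chosen to receive texts so that it fits allocation by clinic.

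The cost is one form item, one table from records already planned and one script line. Sample size, power and visit schedule do not change. The downside is slightly less staff discretion. The change narrows the route without closing it, because the other interviewer judgements remain. The remaining differences between Appendix C and the Study Inclusion and Exclusion lists, item 13 among them, must be reconciled separately.
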